Recent literature has found that burnout is highly prevalent among healthcare professionals, affecting between 40-60% of physicians. [1] The added stressors of the COVID-19 pandemic have also been associated with high rates of multidisciplinary healthcare professional burnout, depression and anxiety, especially among women, nurses, and those working in hospital environments.[2-3] Mental health disorders are also prevalent among health care workers. In a study of 4833 physicians, 41.7% screened positive for depressive symptoms and 6.9% reported having suicidal ideation in the previous year, of whom 27% reported that they would probably or definitely not seek help.[4] The healthcare professionals most in need of care and burnout prevention modalities are those least likely to seek support, with a perceived stigma associated with seeking help.[5] These findings contribute to the mounting body of evidence suggesting there is a significant unmet gap in this vulnerable population.

Healthcare clinicians work in a high-stress environment that requires quick decision making and high levels of both mental and physical acuity. Like other performance careers, a clinician's own mental and physical states are key to their ability to take optimal care of their patients. However, despite the

Last Updated: 2.24.2023

similarities shared with these other performance careers, performance coaching, well-being interventions, and other burnout prevention initiatives are commonly perceived as either ineffective, or out of reach to the health professional workforce due to time restraints, lack of knowledge, or pre-existing stigmas around help seeking. Arena Strive and WHOOP aim to address these barriers by democratizing performance coaching with a seamless asynchronous coaching experience at the clinicians fingertips.

METHODOLOGY

Study design

This study is a prospective randomized controlled longitudinal crossover design with a per protocol analysis integrating one sensor (WHOOP, inc Platform) and one educational intervention (Arena Strive Platform). The **WHOOP** sensor collects **data** on heart rate (HR), heart rate variability (HRV), and sleep data, and will be worn by all participants in the experimental intervention. Participants will be asked to wear the biometric sensor for 12 weeks but will have optional access to the device for a total of 24 weeks.

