Throughout the 12 week intervention period, **participant engagement** within the Arena Strive app will be collected including data points relating to videos/audio watched or listened to, content favorited, or user activities completed. Modifiable activities collected via the Arena Strive Platform include light exposure, light restriction, sleep hygiene, meal timing, and activation and deactivation techniques (yoga nidra, physiological sigh, super O2 breathing).

Self-reported data will also be collected relating to the participants ability to adapt to stress, rest and recover from stress, and self-awareness around these two constructs. WHOOP data, engagement within the Arena Strive app, and self-reported stress adaptability, rest and recovery, and self-awareness will be collected continually throughout the intervention period. The additional self-reported outcomes: professional fulfillment, burnout, self-valuation, and overall satisfaction will be collected by means of an in-app survey at key benchmark moments throughout the intervention period: once at intervention start, again at week 6 following the first phase of the Arena Strive intervention, then again at week 12 following the completion of the experimental intervention period. Participants in the control cohort will follow this same time frame with respect to self-reported surveys. All self-reported data within the control cohort will be collected via identical surveys hosted on Typeform, the web-based surveying platform.

The experimental intervention, 'Arena Strive', will be conducted through the Arena Strive app, self-described as "Healthcare's First Performance Coach". This second-generation platform provides frontline clinicians with a comprehensive journey to access the tools, training, and technology used by other high-pressure fields to increase performance and enhance resilience. Strive uses a dynamic, interactive content platform to bring frontline clinicians the lessons learned, tools, and tailored instruction of world-class performers from elite military, professional athletes, and creative performers. The design will test the effect on measures of professional fulfillment and burnout; self-valuation; satisfaction; and feasibility in full-time NHS clinicians.

Intervention

The experimental intervention employed in this study will be a 12-week, multi-phased approach involving asynchronous learning and coaching experience (6 weeks), and exploration phase (6 weeks).

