Last Updated: 2.24.2023

Phase 1: Enrollment period and participant recruitment, obtain informed consent, complete WHOOP device setup & download Arena Strive app. During the study kickoff, intervention participants can choose to attend coaching workshops with an Arena labs performance coach to learn more about the principles of high-performance medicine, biometric data, and the Arena Strive platform.

Phase 2: In the second phase, a performance coaching platform comprising educational content; data feedback and monitoring; and tailored coaching touchpoints will then be administered via the smartphone application, Arena Strive for a duration of 6 weeks (Arena Strive :: Foundations).Arena Labs performance coaches can be accessed via the app. Arena Labs performance coaches provide personalized coaching tailored to the individual clinician and his/ her unique set of needs. The intervention will also include a wearable biometric device provided by WHOOP to collect physiological data relating to measures of resilience and autonomic function. The accompanying WHOOP app will be available in this phase of the intervention. Data from the wearable device will be passed directly into the Arena Strive app to be summarized and delivered to participants through the app interface for self-monitoring, feedback, and coaching touchpoints.

Phase 3: After 6 weeks of asynchronous guidance through the Arena Strive app, users will then continue the intervention (Arena Strive :: Explorations) with an additional 6 week experience of data feedback.

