As a behavioral intervention, Arena Strive follows the COM-B framework of behavior change, which targets participants' capabilities (C), opportunities (O), and motivations (M) to integrate performance practices into their routines. The first phase of the intervention will involve 6 weeks of micro-learning audio and video content targeting clinicians' capabilities and opportunities to learn and train 17 foundational performance practices. Targeted behavior change techniques (BCTs) help participants overcome barriers, monitor progress, and build intrinsic motivation toward the integration of these 17 practices. These practices leverage techniques and physiological processes that aim to influence the three main foundations of High Performance Medicine: self-awareness, rest & recovery, and stress adaptability. Techniques include but are not limited to autonomic regulation, self-reflection, environmental restructuring, task-based coping, emotion-based coping, guided attention control, and shaping behavior around physiological triggers.

Control Cohort: Participants randomized into the control cohort will receive no intervention for the duration of the experimental intervention. At the conclusion of the full 12 week baseline and intervention period, participants in the control cohort will be given the option to participate in the intervention.

Setting

The study will take place within the Atrium Health Sanger Heart and Vascular Institute, Emergency Department, Surgery and Pulmonary Critical Care.. All data collection, intervention, and participant interaction will take place asynchronously through the Arena Strive smartphone application, and the WHOOP wearable biometric device.

Expected Start Date

The expected enrollment will begin on January 2023 for both cohorts.

Last Updated: 2.24.2023

Duration of Study

The total length of this study will be 24 weeks from participant recruitment to conclusion of data analysis.

- 6 weeks = Phase 1 Enrollment period and participant recruitment, obtain informed consent, complete WHOOP device setup & download Arena Strive app.
- 6 weeks = Phase 2: Arena Strive Intervention period (Arena Strive :: Foundations)
- 6 weeks = Phase 3 Continue WHOOP device & Arena Strive Intervention (Arena Strive :: Explorations)
- 6 weeks = Data analysis

Study Participants

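### The protocol requires no WHOOP nights before the intervention and defines no biometric baseline or time zero, and its statements on wear conflict

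*Combined protocol and SAP*

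**What the plan says.** **Wear and intervention length.** Study design: "Participants will be asked to wear the biometric sensor for 12 weeks", with optional access to the device up to 24 weeks. Intervention: a "12-week, multi-phased approach involving asynchronous learning and coaching experience (6 weeks), and exploration phase (6 weeks"). Study design also says that WHOOP data, with app engagement and some self-reports, "will be collected continually throughout the intervention period".

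**The device as part of treatment.** Under Phase 2 in the Intervention section: "The intervention will also include a wearable biometric device provided by WHOOP". Its data are fed back to participants through the Strive app.

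**What precedes the intervention.** Duration of Study: "6 weeks = Phase 1 Enrollment period and participant recruitment, obtain informed consent, complete WHOOP device setup & download Arena Strive app". No wear, run-in or minimum number of nights is attached to this phase.

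**Statements that point elsewhere.** The Control Cohort paragraph begins a sentence "At the conclusion of the full 12 week baseline and intervention period", which places a baseline inside the 12 weeks. The inclusion criteria in Study Participants ask for willingness to wear WHOOP for the whole study, and Duration of Study counts the study as 24 weeks from recruitment.

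**Who wears it.** Study design says the sensor "will be worn by all participants in the experimental intervention". Data Collection says that control data collection mirrors the experimental arm, with a few exceptions.

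**Analysis.** Data Analysis plans multilevel models of sleep, HRV and RHR across time by condition, with random intercepts and slopes. It mentions that people may differ at baseline but does not define baseline. The surveys, by contrast, have a stated first measurement at intervention start.

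**The concern.** Nine of the listed primary outcomes come from the WHOOP strap, and the outcome table gives their timing only as continuous. If requested wear and the intervention are the same 12 weeks, every required night in the experimental arm is a treated night.

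Three things are then lost:

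- the pre-intervention value of each outcome, usually the best covariate for precision in a trial of at most 100 people;
- any check that the arms were alike on these outcomes before treatment;
- a clean starting point for the time trend. An effect that appears in the first days raises the experimental arm's starting level and leaves little for the slope to show.

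Random intercepts do not replace a baseline. They are estimated from the same treated nights, and the condition term is still judged against the full between-person variation.

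**Working it through.** **1. The timeline.** Inputs are from Duration of Study, Study design and Intervention.

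- Total: 6 + 6 + 6 + 6 = 24 weeks, which reproduces the stated length.
- Intervention: 6 + 6 = 12 weeks, as stated.
- Requested wear: 12 weeks. If these are the intervention weeks, required pre-intervention wear is 12 − 12 = 0 weeks.

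**2. The readings side by side.**

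| Source | Wear before Strive starts |
|---|---|
| Study design and Intervention | 0 weeks |
| Control Cohort paragraph | Some, but inside the 12 weeks, so fewer than 12 weeks of intervention; contradicts 6 + 6 |
| Inclusion criterion on wear | From set-up in Phase 1, so anything from 0 to 6 weeks depending on enrolment date; exceeds the 12 weeks requested |

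These cannot all hold. None gives a baseline window or says that Phase 1 nights will be analysed.

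**3. What a slope would capture.** Assume the effect rises linearly to its full size over R weeks and then stays there, and fit a least-squares line over T = 12 weeks. With x = R/T, the fitted 12-week rise as a share of the full effect is 3x − 2x².

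- Immediate effect, x = 0: 0%.
- Two-week ramp, x = 1/6: 0.500 − 0.056 = 0.444, or 44%.
- Six-week ramp, x = 1/2: 1.5 − 0.5 = 1.0, or 100%.
- Twelve-week ramp, x = 1: 3 − 2 = 1.0, or 100%.

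A least-squares fit to 84 simulated nights gives the same four values. The shapes are assumptions; the documents give none.

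**4. Precision, illustration only.** The documents contain no power calculation to reproduce. Take the maximum of 100 participants at 2:1, about 67 and 33 (Study Participants). Assume that the controls have WHOOP data and that one two-group comparison of means is made at two-sided 0.05 with 80% power.

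- Without baseline: (1.960 + 0.842) × √(1/33 + 1/67) = 2.802 × 0.2127 = 0.596 SD.
- With a baseline covariate of correlation r, multiply by √(1 − r²):
  - r = 0.6: 0.596 × 0.8 = 0.48 SD
  - r = 0.7: 0.596 × 0.714 = 0.43 SD
  - r = 0.8: 0.596 × 0.6 = 0.36 SD

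The variance reduction is r², or 36% to 64% over this range. The correlations are assumed. The planned model uses repeated measures, so these figures show the order of the gain and do not give the trial's power.

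**The case against.** **Phase 1 nights may exist.** Set-up is completed in Phase 1, and the inclusion criterion implies wear for longer than 12 weeks. No section says outright that the 12 wear weeks are exactly Phases 2 and 3. This stands: the documents do not show that no pre-intervention night will be recorded. But no section requires, defines or uses such nights, so the objection adds a contradiction and does not supply a baseline.

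**Randomisation makes a baseline unnecessary.** If controls wear WHOOP, levels can be compared between arms without bias, and an immediate effect would appear in the condition term. This also stands. What is lost is precision, the balance check and whatever the slope alone would miss. If controls do not wear WHOOP, there is no between-arm biometric comparison to protect, and the precision illustration falls away.

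**A stronger reading.** A reader might infer that the models take their baseline from early treated nights, and that a baseline from weeks 1–2 would absorb 17% of an effect building over six weeks, 50% of one complete at two weeks and 100% of an immediate one. The documents do not support this. Data Analysis plans no change score from early nights; it leaves baseline undefined. The treated-nights description could in any case apply only to the experimental arm.

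**Phase 1 nights may not be untreated.** Optional coaching workshops take place at kickoff, and the benefits section credits access to WHOOP data itself with better sleep, HRV and RHR, although at four months. This is fair, and the fix has to deal with it.

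**Conclusion.** The point holds as a gap in specification together with a contradiction. No pre-intervention WHOOP nights are required, no biometric baseline or time zero is defined, and the wear statements in Study design, Intervention (including its Control Cohort paragraph) and the inclusion criteria must be reconciled. On the natural reading, the experimental arm has no untreated reference nights.

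The size depends on matters that the documents leave open. The loss of early effects (0% captured if immediate, about 44% for a two-week ramp, essentially none lost for six weeks or longer) applies only if inference rests on a linear condition-by-time slope, which the plan does not say. The gain from about 0.60 SD to 0.48–0.36 SD needs about 33 controls with WHOOP data and correlations of 0.6 to 0.8, neither of which the documents establish. It would go too far to say that the planned between-arm analysis is biased for want of a baseline. The change is worth making because it costs little and helps whichever way control wear is settled.

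**What to change.** - Reconcile the wear statements, and state whether controls wear WHOOP.
- Use the Phase 1 set-up window to collect a defined pre-intervention baseline, for example 14 nights, before Strive content and kickoff workshops begin and, where feasible, before participants see their data. If feedback cannot be withheld, say so.
- Apply the same window to any control who wears the device.
- Set time zero at Strive start, with the matching date for controls.
- Include the mean of the baseline nights as a covariate, or the nights themselves as pre-period data, in every biometric model. State which term carries the inference: the condition difference in level, the condition-by-time slope, or both.
- Say how participants with too few baseline nights will be handled.

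The cost is up to two more weeks of wear, within the six-week Phase 1 and the 24 weeks of device access, and a later programme start for people who enrol near the end of Phase 1.

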Participant Consent: All participants involved in this study will be required to provide written consent to participate. Participants will be asked to consent to the collection of self-reported data provided through in-app and digital surveys as well as biometric data collected through the WHOOP device. A copy of the written consent form is included in the appendix. Spanish language consents will be made available upon request.

Equipment/Supplies/Services

All equipment, services, and supplies related to the study intervention will be provided by Arena Labs, and WHOOP. All equipment, services, and supplies related to the recruitment of study participants will be provided by the Atrium Health team.

Data Collection

All study data will be collected via an in-app or online survey, through app interactions, or through the WHOOP wearable biometric device. Data collection for the control cohort will mirror that of the experimental group in both frequency and content with a select few exceptions. Control cohort participants will not receive questions relating to feasibility and satisfaction, and self-reported data will be collected via online surveys hosted on Typeform. A breakdown of the primary and secondary outcome variables are summarized below.

		Outcome Variable	Instrument	Collection Method
Primary Outcomes	Self Reported	Professional Fulfillment & Burnout	Stanford Professional Fulfillment Index (PFI)	Onboard, midpoint, and exit Survey
		"Gold standard" for measuring burnout	Maslach Burnout Inventory (MBI)	Onboard, midpoint, and exit Survey
		Self Valuation	Stanford Self Valuation Scale	Onboard, midpoint, and exit Survey
	Biometric Data	HRV	WHOOP Strap	Continuous
		SWS %	WHOOP Strap	Continuous
		REM %	WHOOP Strap	Continuous
		RHR	WHOOP Strap	Continuous
		Awake Time	WHOOP Strap	Continuous
		Light Sleep Duration (%)	WHOOP Strap	Continuous

		Sleep Disturbances	WHOOP Strap	Continuous
		Sleep Debt	WHOOP Strap	Continuous
		Sleep Consistency	WHOOP Strap	Continuous
Secondary Outcomes	Self-reported	Satisfaction	Client Satisfaction Questionnaire-8 (CSQ-8)	Exit Survey
		Feasibility/Adherence	NA	In-app Survey & app engagement

Data Analysis

- We will use t-tests in SPSS to compare the primary outcome measures across the experimental and control groups.

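### The first PFI, MBI and self-valuation survey follows allocation (and app installation in the experimental arm), so it is not a clean pre-randomisation baseline

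*Combined protocol and SAP*

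**What the plan says.** The Study design section says that professional fulfillment, burnout and self-valuation "will be collected by means of an in-app survey at key benchmark moments throughout the intervention period". The occasions are "once at intervention start, again at week 6 following the first phase of the Arena Strive intervention", and then week 12. For the control arm, "Participants in the control cohort will follow this same time frame with respect to self-reported surveys", and "All self-reported data within the control cohort will be collected via identical surveys hosted on Typeform, the web-based surveying platform". The Data Collection table lists all three scales as primary outcomes with the collection method "Onboard, midpoint, and exit Survey".

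The Intervention section describes the steps before coaching starts: "Phase 1: Enrollment period and participant recruitment, obtain informed consent, complete WHOOP device setup & download Arena Strive app". In the same paragraph it adds: "During the study kickoff, intervention participants can choose to attend coaching workshops with an Arena labs performance coach". Platform coaching starts in Phase 2. Under Control Cohort, controls receive no intervention during that time.

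The documents do not date randomisation, and they place no survey before it. The Objectives section states the primary outcome as increases in resilience measures and decreases in burnout measures. The Data Analysis section plans t-tests of the primary outcome measures between arms, and names no time point, change score or baseline covariate.

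**The concern.** A baseline measured before randomisation cannot be affected by treatment or by knowledge of allocation. Any difference between arms at that point is chance, and adjusting for it only helps. A first survey taken after allocation lacks this protection.

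Here, controls would answer knowing that they receive nothing for 12 weeks. Experimental participants would answer knowing that they have the programme, with the app on their phone and perhaps after a workshop. Fulfillment, burnout and self-valuation are self-rated, so expectation or disappointment can move the answers without any change in well-being.

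The direction cannot be predicted. Early optimism in the experimental arm, or disappointment in controls, would make the experimental arm look better at the start and so hide benefit. Experimental participants who rate their burnout as worse because they expect to improve would create apparent benefit. Either shift would pass into any analysis that subtracts the first survey or adjusts for it.

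**Working it through.** **Timing, from the text**

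1. The survey mode depends on the arm: in-app for the experimental arm, Typeform for controls. The arm must be known before the first survey is sent, so the survey follows allocation.
2. An in-app survey needs an installed app, so in the experimental arm it also follows installation, which the protocol puts in Phase 1.
3. The week-6 survey follows the first 6-week phase of the intervention. The start of the intervention is therefore most naturally the start of Phase 2, after Phase 1.
4. The workshops are described under Phase 1, for intervention participants only. No sentence orders them against the first survey. An onboarding survey could come before or after a workshop.

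**Size of the bias**

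The plan gives no alpha, power, SD, effect size or sample-size calculation, so there is no figure of its own to reproduce. What follows is illustration under stated assumptions. Scores are in SD units with higher meaning better, and the SD is the same at each survey. Let D be the true week-12 difference (experimental minus control), d the difference between arms in the first survey caused by its timing, and r the correlation between first and week-12 scores.

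- Week-12 scores alone: expected estimate D, with no bias.
- Change scores: expected estimate D − d, so the bias is d in size.
- Baseline-adjusted (ANCOVA): expected estimate about D − r × d, so the bias is about r × d in size.

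With d = 0.1 to 0.3 and r = 0.6, the bias is 0.10 to 0.30 SD for change scores and 0.06 to 0.18 SD after adjustment.

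Both directions, with r = 0.5 to 0.7:

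| Assumed D | Assumed d | Change-score estimate | ANCOVA estimate |
|---|---|---|---|
| 0.5 | 0 | 0.50 | 0.50 |
| 0.5 | +0.2 | 0.50 − 0.20 = 0.30 | 0.40 to 0.36 |
| 0.5 | −0.2 | 0.50 + 0.20 = 0.70 | 0.60 to 0.64 |
| 0 | −0.2 | 0.20 | 0.10 to 0.14 |

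For D = 0.5 at 67:33, with an assumed two-sided alpha of 0.05, a shift of +0.2 lowers power as follows:

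- Change scores: from 65–86% to 29–45%.
- ANCOVA: from 78–91% to 58–66%.

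**Cost of ignoring the first survey**

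The Study Participants section caps enrolment at 100, allocated 2:1, so about 67:33 at best. With 80% power and two-sided alpha 0.05 (both assumed), the smallest detectable difference is:

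- Week-12 scores alone: (1.960 + 0.842) × √(1/33 + 1/67) = 2.802 × 0.2127 = 0.60 SD.
- Change scores: 0.596 × √(2(1 − r)) = 0.60, 0.53 and 0.46 SD for r = 0.5, 0.6 and 0.7.
- ANCOVA: 0.596 × √(1 − r²) = 0.52, 0.48 and 0.43 SD for the same r.

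A clean baseline used as a covariate therefore brings the detectable difference down from 0.60 SD to between 0.43 and 0.52 SD.

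**The case against.** The strongest reply is that the plan specifies no analysis that the shift would harm. Data Analysis names only t-tests between arms. The protocol never calls the first survey a baseline, and the increases and decreases in the Objectives can be read as the expected direction of effect. This stands in part: a t-test on week-12 scores is immune. But the plan names neither the time point nor the form of the t-test. A change-score t-test would fit its wording, and would fit an objective framed as changing these measures. The immune option also gives up precision that a trial of at most 100 can ill afford.

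Second, a reader might infer that the experimental arm's first scores were taken after coaching. The documents do not support that:

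- The order of survey and workshop is not written.
- The workshops are optional and described as introductory.
- Installing an app is not shown to be treatment, and the coaching platform is delivered from Phase 2.
- The 6 weeks of Phase 1 are a recruitment window, not a stated exposure for each person.

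What stands is timing after allocation and installation, with workshop exposure as a possibility.

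Third, one might infer that only the experimental arm can lose its first survey, because someone may never open the app. A control who never opens the Typeform link loses it too, so this is not a one-sided defect.

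Fourth, if knowing one's arm shifts reporting by a lasting amount, a survey after allocation would partly cancel that shift in a change score. This is true, but the cancellation requires a stable shift, which nobody could verify. It would also remove any real early effect.

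Finally, moving only the first survey to Typeform would make the experimental arm alone change mode between baseline and follow-up. That is a fair criticism of a partial remedy, and the follow-up mode has to be settled with it.

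**Conclusion.** The concern holds in a limited form. As written, the first survey follows allocation in both arms and app installation in the experimental arm. That follows from the arm-specific survey modes and can be held with high confidence. That it also follows the kickoff workshops is plausible but not stated.

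The harm is conditional. It arises if the primary comparison uses change scores (bias d) or baseline adjustment (bias about r × d), in either direction. The values of d, r, D, alpha and power used here are all assumptions, and nothing in the documents shows that d is large or even non-zero. The figures show sensitivity; they do not estimate the error in this trial. If the sponsor commits to an unadjusted week-12 comparison there is no bias from this source, only the loss of precision.

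The change should be made: it is cheap, removes a source of bias that later analysis cannot reliably undo, and gives a valid covariate.

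**What to change.** Amend Study design and the Data Collection table, and re-order Phase 1:

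1. After consent and before randomisation, all participants complete the PFI, MBI and self-valuation survey on the Typeform version already planned for controls.
2. Only then are the allocation, app, device and workshop invitation released.
3. At weeks 6 and 12 both arms complete these scales on Typeform, so that neither arm changes mode between baseline and follow-up.
4. In Data Analysis, state that the primary comparison of each scale adjusts for its pre-randomisation score as a covariate, and name the time point.

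Suggested wording: *All participants will complete the PFI, MBI and Self Valuation Scale on Typeform after consent and before randomisation. Allocation will be disclosed, and app, device and workshop access given, only once this survey is complete. Both arms will complete the same Typeform surveys at weeks 6 and 12.*

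The cost is a wording change, a re-ordering of enrolment steps and a small change to the analysis text. No instrument or survey occasion is added. There are two small downsides: volunteers who do not complete the survey are not randomised, and experimental participants answer the benchmark surveys outside the app.
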